### ***Treatment Period***

Upon receipt of the study product, the subjects will re-confirm their eligibility to continue in the study based on the previous screening criteria including completion of the WURSS-21 questionnaire (see appendix section 15.2.1). Those with nasal congestion (described as plugged nose on WURSS-21) of at least moderate (score 5) based on WURSS-21 and who exhibit at least one other common cold symptom of at least mild (score 3) based on WURSS-21 and who self-select to treat their nasal congestion symptoms, will be asked to start treatment with the product according to the label instructions.

Subjects who do not satisfy these criteria will be considered dropouts.

Each morning the subject will be prompted to complete the WURSS-21 questionnaire, the additional QoL questions (considering the effects of the product used during the day before).

### ***End of Treatment Period***

As per leaflet instruction, xylometazoline hydrochloride (0.1%) nasal spray may be used for up to 7 treatment days.

Subjects will have the option to discontinue treatment at their discretion. The reasons for discontinuing treatment will be captured in the app whenever possible.

Subjects may choose to discontinue treatment if:

- they feel that their symptoms do not warrant further use of the study product
- their nasal symptoms/congestion is considered resolved

Subjects that continue to use the study product will be prompted to discontinue treatment after 7 days of continuous use and seek advice from their general practitioner for further assessment and treatment.

Subjects will also be informed that the study will end on Day 7 (or the day after the last treatment, if earlier than 7 days), and will be asked to fill in an exit survey.

## **4.2 Scientific Rationale for Study Design**

RWE studies reflect product use in everyday life. They offer the opportunity to gather information on currently marketed products to not only substantiate clinical evidence, but to provide additional information on the target patient population.

The Wisconsin Upper Respiratory Symptom Survey (WURSS) is an evaluative illness-specific quality of life instrument, designed to assess the negative impact of acute upper respiratory infection, presumed viral (the common cold). WURSS-21 is the short version of this validated survey.

Subjects with nasal congestion due to common cold, who seek to treat with study treatment (Otrivine) will complete WURSS-21 and an additional GSK CH designed QoL

Property of GSK Consumer Healthcare - Confidential

May not be used, divulged, published or otherwise disclosed without the consent of GSKCH

questionnaire once every 24-hours. Study treatment use will be reported via diaries. These measures will provide GSK CH with information on the effects of Otrivine over the natural course of their common cold. This will enable GSKCH to evaluate the daily effects that may be attributable to the study treatment.

#### Limitations of the study

Given the natural course of the common cold, data collected during this study may be confounded by the natural resolution of the disease. Within 24 hours of cold onset, most patients report an escalation in the number of symptoms they experience, including sore throat, nasal congestion, runny nose, and headache. Over the initial days of having a cold, sore throat appears to be most bothersome on day 1 followed by nasal congestion on days 2 to 5 and cough on days 6 and 7.

Given the natural course of the disease, making sure subjects have access to treatment when nasal symptoms are at their peak will allow for subsequent QoL data capture, reducing the influence of confounding variables.

There is substantial evidence to show that different symptoms of common cold overlap during the natural course of the disease. Subjects may likely be using over-the-counter antipyretics/analgesics for fever and/or headache, which may influence their overall QoL and confound data collected. During this study patients will be prompted to report medications they take for symptom relief, along with any changes in medication over the course of their study participation, which will allow the study team to review collected data objectively.

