### **5.4 Randomization Criteria**

There is no randomization in this study. All enrolled subjects will be provided with the same study product.

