### **12.3.1 Primary Analysis**

For the primary objective, measurements of health related QoL indicators and cold symptoms will be evaluated using total scores, QoL domains scores, symptom domains scores and single domains scores using the WURSS-21 questionnaire pre and post treatment to determine the effect of Otrivine on QoL factors and cold symptoms. Change in mean WURSS-21 scores from pre and post treatment will be summarized for each study day and analyzed using a Student's paired t-test. If data are found to be non-normal a non-parametric Hodges-Lehmann test will be used.

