### **12.3.2 Secondary Analysis**

For the secondary objective, subjects' pre-treatment score will be used to determine the effect of Otrivine on additional QoL parameters. Median post-treatment scores will be presented for each day of treatment through Day 7 or until data are no longer provided due to nasal symptom resolution, whichever comes first.

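### Sections 12.3.1 and 12.3.2 say an uncontrolled pre-post comparison will determine the effect of Otrivine; the mitigation offered in Section 4.2 is at most partial and cannot separate the product from natural recovery

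*Protocol*

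**What the plan says.** The limitations text in Section 4.2 states that "data collected during this study may be confounded by the natural resolution of the disease". After describing the course of a cold, it says that ensuring access to treatment "when nasal symptoms are at their peak will allow for subsequent QoL data capture, reducing the influence of confounding variables".

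Section 12.3.1 evaluates WURSS-21 scores "pre and post treatment to determine the effect of Otrivine on QoL factors and cold symptoms", using a paired test of the change on each study day. Section 12.3.2 says the subject's "pre-treatment score will be used to determine the effect of Otrivine on additional QoL parameters", and adds: "Median post-treatment scores will be presented for each day of treatment through Day 7". It names no test.

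Section 5.4 states: "There is no randomization in this study. All enrolled subjects will be provided with the same study product". Section 6.5 confirms that the study is open label. Under Section 5.2, plugged nose must score at least 5 at screening (criterion 4) and again around product receipt (criterion 6).

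**The concern.** The sentence in 4.2 opens by referring to the natural course of the disease, so a reader will take it as the answer to the confounding just conceded. Starting treatment near the peak does not provide that answer. Once the peak has passed, scores fall with or without the product, and subjects chosen for a high score tend to score lower next time.

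Section 12 then assigns the whole pre-post change to the product and does not carry the caveat forward. A paired test is valid for its own null of zero mean change, but rejecting that null does not identify the cause. Followed as written, a significant fall in 12.3.1 could be reported as Otrivine's effect, and 2.2 says the sponsor seeks to demonstrate just such an improvement.

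**Working it through.** **1. The plan's own sample size.** Inputs from 12.1: alpha 0.05, power 80%, standardized effect 0.27, dropout 20%.
- Normal approximation, two-sided (sidedness is not stated): (1.960 + 0.842)² / 0.27² = 107.7.
- Divided by the Wilcoxon relative efficiency: 107.7 / (π²/9) = 98.2, so 99 (logistic); 107.7 / (3/π) = 112.7, so 113 (normal).
- Dropout: 100 / (1 − 0.20) = 125.

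The stated 100 completers fit one conventional variant and 125 follows exactly. This neither supports nor weakens the point.

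**2. What the timing can and cannot do.** Section 4.2 gives the most bothersome symptom as sore throat on day 1, "followed by nasal congestion on days 2 to 5 and cough on days 6 and 7". Section 2.2 puts maximum nasal severity at days 2 to 3. The delivery time is not stated. Assume Day 0 falls on day 2 or 3 of the cold:
- Day 0 = cold day 2: cold day 5 is study Day 3, so Days 4 to 7 (four of seven reports) lie past the congestion period.
- Day 0 = cold day 3: cold day 5 is study Day 2, so Days 3 to 7 (five of seven) lie past it.
- Allowing one day for the 24-hour recall, three or four of the seven remain past it.

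The first reports may therefore see little natural nasal decline. The later ones are not protected.

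**3. What a rejection means with no product effect.** Two-sided paired t-test; d is the natural improvement in SDs of change, an assumption because the protocol gives no untreated change. P = probability that |T| exceeds the critical value, where T is noncentral t with n − 1 df and noncentrality d√n.
- n = 100, d = 0.27: noncentrality 0.27 × 10 = 2.70, critical value 1.984, P = 0.76.
- n = 60, d = 0.27: noncentrality 0.27 × 7.746 = 2.09, critical value 2.001, P = 0.54.
- n = 100, d = 0.10 / 0.20 / 0.50: P = 0.17 / 0.51 / 0.999.

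The value n = 60 is an assumption standing for later days. Under 8.2.1, subjects who stop early report only through one day after their last dose, so later days have fewer pairs.

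**4. Regression to the mean on the plugged-nose item.** All inputs are assumptions: mean 4 to 5, SD 1.6, reliability 0.5 to 0.85, scores rounded and clipped to 0 to 7, subjects kept if the screening and Day 0 scores are both at least 5, and no decline or product effect afterwards. Simulated standardized improvement (3,000,000 draws per setting):

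| Trend after screening | Baseline = Day 0 | Baseline = screening |
|---|---|---|
| None | 0.13 to 0.46 | 0.13 to 0.46 |
| Rise of 0.3 to 0.5 points | 0.07 to 0.39 | −0.31 to 0.30 |

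The last cell matters because Table 1-1 places the baseline WURSS-21 at screening, within 24 hours of onset under criterion 5. By 4.2, "Within 24 hours of cold onset, most patients report an escalation in the number of symptoms they experience". From that score, untreated subjects may worsen first.

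**The case against.** **The limitation is disclosed.** This stands. Section 4.2 states it under its own heading and elsewhere speaks only of effects that may be attributable to treatment. A reader might infer that the protocol conceals the problem; it does not. The fault is the mitigation claimed and the unqualified purpose stated in Section 12. The SAP may add detail, but those are statements in the protocol.

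**The mitigation is partly right.** This also stands. The sentence speaks of reducing confounding, not removing it, and of confounding variables in the plural. It may hold for other symptoms, and starting within the congestion period can limit natural nasal decline on the first days. The stronger reading, that peak timing does nothing about natural resolution or makes it worse throughout, is not supported.

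**The bias need not favour the product.** Correct. A reader might infer that every day and item is tilted towards Otrivine. Early days, later-peaking items such as cough, and a screening baseline can go the other way. The direction varies; the inability to attribute the change does not.

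**The figures are a generic power curve.** They are, and the simulation covers one item only. They illustrate; the conclusion does not rest on them.

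**Section 12.3.2 has no test.** True, so the risk of a significant result being misread arises only from 12.3.1. The causal wording is the same in both.

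**Conclusion.** The point holds as a matter of wording and interpretation. A single open-label arm compared with its own pre-treatment score can describe change during use; it cannot determine the product's effect, and treatment near the peak does not alter that. This follows from the design and needs no numerical assumption.

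The size of the untreated change is not in the protocol, and for early days or a screening baseline neither is its direction. The 76% (100 pairs) and 54% (60 pairs) assume a natural improvement of 0.27 SD, a two-sided paired t-test and zero product effect. They should not be read as the trial's false-positive rate. Nor do the documents support reading the point as a case against single-arm real-world studies or as a demand for a control arm: the design is openly stated, and the remedy is to match the stated conclusion to it.

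**What to change.** - **Section 4.2:** delete the closing clause about confounding variables and add: *This does not separate the effect of the product from natural resolution or from regression to the mean after selection on plugged nose >=5; some improvement over the week is expected without treatment.*
- **Sections 12.3.1 and 12.3.2:** replace the stated purpose of determining an effect with: *to describe change from the pre-treatment score during use of Otrivine in* the respective outcomes.
- **Section 12.3.1:** add that p-values against zero change do not by themselves support attribution to the product.
- **Sections 1.1, 2.1, 2.2 and Table 3.1:** align the rationale and objectives. Otherwise the analysis would describe change while the primary objective still claims to evaluate effects.

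The cost is wording only: no new data, test, sample size or arm. The downside is a permitted conclusion weaker than the goal stated in 2.2.

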### **4.3 Justification for Dose**

Dosing instructions will be followed as listed on the study product commercial label.

### **4.4 End of Study Definition**

A subject is considered to have completed the study if they have completed all procedures and assessments of the study including the last scheduled procedure shown in the Schedule of Activities.

Subjects will have the option to discontinue treatment at their discretion, if they determine they no longer want treatment. The reasons for discontinuing treatment will be captured in the app whenever possible. The end of this study per subject is tentatively defined as Day 7 but may vary based on the need/severity of nasal congestion (see section 4.1 for further details). At the end of study each subject should complete an exit survey including product satisfaction and intent to repurchase.

## 5 STUDY POPULATION

### 5.1 Type and Planned Number of Subjects

Adult subjects aged 18 years and over, displaying cold symptoms will be screened for enrollment into the study. This study intends to enroll approximately 125 eligible subjects. This study assumes an approximate 20% drop out rate. A total of 100 subjects are expected to complete the study.

The common cold has an acute onset and limited duration. Hence subjects who have been displaying cold symptoms over no longer than the previous 24 hours will be further screened for eligibility and enrollment in the study. Subjects that confirm their common cold symptoms within 24 hours of receiving the study product will be enrolled into the study. Subjects who do not meet the eligibility criteria will be considered screen-fails and withdrawn from the study.

This study can fulfill its objectives only if appropriate subjects are eligible. The following inclusion/exclusion criteria are designed to select subjects for whom participation in the study is considered appropriate. All relevant medical and non-medical conditions will be taken into consideration when deciding whether a subject is suitable for this protocol.

### 5.2 Inclusion Criteria

An individual must meet all the following inclusion criteria to be enrolled in the study:

1. Individual's provision of a signed and dated eIC form indicating that the subject has been informed of all pertinent aspects of the study before any assessment is performed.
2. Individual is 18 years of age or older at the signing of the informed consent.
3. Individual reporting a nasal congestion, and at least another common cold symptom among runny nose, sore throat, cough.
4. Individual reporting a minimum score of 5 (moderate) for plugged nose associated with common cold symptoms and at least one other symptom of common cold (at least mild score of 3) as per the WURSS-21 questionnaire at screening.
5. Individual reporting initiation of cold symptoms within no longer than 24 hours of prior to initiation of screening.
6. Individuals confirm common cold symptoms within 24 hours of study product receipt of minimum score of 5 (moderate) for plugged nose associated with common cold symptoms and at least one other symptom of common cold (at least mild score of 3) as per the WURSS-21 questionnaire
7. Male and female individuals
8. Individual that owns a smart device and willing to download the study app
9. Individual who is willing and able to complete all activities as shown in the [Schedule of Activities](#) independently on own smart devices.
10. Individual is in good general and mental health.

Property of GSK Consumer Healthcare - Confidential

May not be used, divulged, published or otherwise disclosed without the consent of GSKCH

CCI

Clinical Protocol Template v9.0

11. Individual who has a self-reported medical diagnosis of cardiovascular disease (including those with long QT syndrome), hyperthyroidism or diabetes mellitus, may be included if deemed acceptable by a medically qualified investigator.
12. Individual who is showing a strong reaction to adrenergic substances, as manifested by signs of insomnia, dizziness, tremor, cardiac arrhythmias, or elevated blood pressure, may be included if deemed acceptable by a medically qualified investigator.

### **5.3 Exclusion Criteria**

An individual who meets any of the following exclusion criteria will be excluded from the study:

1. Individuals under 18 years of age.
2. Individuals who are allergic to xylometazoline hydrochloride or any of the other ingredients in the spray (see product label).
3. Individuals who have had recent neurosurgery.
4. Individuals who self-report narrow angle glaucoma, chronic nasal inflammation with very dry nasal passages (rhinitis sicca or atrophic rhinitis), or enlarged prostate gland.
5. Individuals who self-report a rare tumor of the adrenal gland that produces high amounts of adrenaline and noradrenaline (phaeochromocytoma).
6. Individuals who are taking monoamine oxidase inhibitors (MAOIs) or have stopped taking them in the last 14 days.
7. Individuals who are pregnant, lactating, or plan to be pregnant or lactating during the course of the study.
8. Individual who is currently using or has used a nasal decongestant (i.e. adrenergic, steroids) within the last 7 days (or for more than 7 days) prior to initiating study treatment.
9. Individuals who have tested positive for COVID-19 within one month prior to enrollment into the study.
10. Individuals who have taken a vaccine one week prior to enrollment into the study.

### **5.4 Randomization Criteria**

There is no randomization in this study. All enrolled subjects will be provided with the same study product.

### **5.5 Lifestyle Considerations**

As a real-world evidence study, there will be no lifestyle considerations.

## 5.6 Screen Failures

Screen failures are defined as subjects who consent to participate in the study but are not subsequently enrolled in the study i.e., do not fulfill all the screening criteria.

To ensure transparent reporting of screen failure subjects, a minimal set of screen failure information will include demography (year of birth, gender, race), screen failure details (e.g., withdrawal of consent), and eligibility criteria.

Prospective subjects who do not meet the criteria for enrollment in this study (screen failure) may not be re-screened unless due to technical issues within the study app/portal. If re-screening is applicable, individuals will be re-invited with a new subject ID.

## 5.7 Sponsor's Qualified Medical Personnel

Contact information for the sponsor's appropriately qualified medical personnel for the study is documented in the Study Contact List held by CCI [REDACTED]

To facilitate access to appropriately qualified medical personnel on study-related medical questions or problems, subjects will be provided with contact information in the CCI [REDACTED] app or will be able to use the chat function in the study app.

# 6 STUDY PRODUCT

## 6.1 Study Product Supplies

The following study products will be supplied by the Clinical Supplies Department, GSK CH or preferred vendor. Subjects will be instructed to return the study product after treatment discontinuation or on Day 7 in a self-addressed envelope/packet.

**Table 6-1 Study Product Supplies**

	Test Product
Product Name	Otrivine Congestion Relief 0.1% Nasal Spray (Xylometazoline Hydrochloride), Menthol (UK Marketplace)
Pack Design	Labelled commercial pack
Dispensing Details	One labelled pack shipped to subject upon completion of baseline assessments and questionnaires
Product Master Formulation Code (MFC)	CCI [REDACTED]
Dose/Application	As per label and leaflet instructions: 1 spray in each nostril up to 3 times per day until resolution of symptoms or up to a maximum of 7 days, whichever occurs first.

Property of GSK Consumer Healthcare - Confidential

May not be used, divulged, published or otherwise disclosed without the consent of GSKCH

CCI [REDACTED] Clinical Protocol Template v9.0

Route of Administration	Nasal Spray
Usage Instructions	As per directions stated on the label and Leaflet
Return Requirements	All used/unused samples to be returned

## 6.2 Administration

Only subjects enrolled in the study may receive study products. Product shipments to subjects will be tracked and subjects will be asked to confirm that they have received the product via the **CCI** [REDACTED] app. The app will also advise subjects to follow the label and leaflet and confirm the first use of the product.

### 6.2.1 Medication/Dosing Errors

Medication/dosing errors may result, in this study, from the administration or consumption of:

- the wrong product,
- by the wrong subject,
- at the wrong time,
- or at the wrong dosage.

In the event of medication dosing error, the sponsor should be notified **immediately and under no circumstance should this exceed 24 hours** and information should be captured in the electronic case report form (eCRF).

If a medication/dosing error is accompanied by an AE, as determined by the investigator, the medication/dosing error and, any associated AEs are to be captured in the eCRF AE form.

### 6.2.2 Overdose

An overdose is a deliberate or inadvertent administration of a product at an amount higher than specified in the protocol.

Overdose is not likely to occur in this study.

## 6.3 Study Product Storage

Subjects will be instructed to:

- Keep this medicine out of sight and reach of children.
- Store the product below 25°C.

Property of GSK Consumer Healthcare - Confidential

May not be used, divulged, published or otherwise disclosed without the consent of GSKCH

**CCI** [REDACTED] Clinical Protocol Template v9.0

- Store the product in its original package.
- Not dispose this medicine via wastewater or household waste.

## 6.4 Study Product Accountability

All products supplied are for use only in this clinical study and should not be used for any other purpose.

**CCI** preferred distributing vendor must maintain adequate records documenting the receipt, shipment, loss, or other disposition of all the product supplies.

**CCI** preferred distributing vendor is responsible for accountability, reconciliation, and record maintenance of study products stored/non-dispensed at the vendor site.

### 6.4.1 Destruction of Study Product Supplies

At the end of the study, the investigator/designee, and a representative of GSK CH (study monitor) or designated vendor will inventory all used and unused study products. The study product accountability record for returned study products will then be completed. All study product (used and unused) for this clinical study, will be returned for destruction to the GSK CH Clinical Supplies Department or designated vendor using the return instructions provided. Detailed instructions for the return of study product for the accountability checks and subsequent destruction will be provided by GSK CH during the study in time for study close out visit.

